4.2. Definition of Baseline

Baseline is defined as the data most recently collected prior to the administration of study treatment except for Best Corrected Visual Acuity (BCVA) letter score.

Best corrected visual acuity assessment is conducted in duplicate. For the BCVA letter score (derived from the Early Treatment Diabetic Retinopathy Study [ETDRS]), baseline for the TE and CE is defined as the value which corresponds to the most recent and best visual acuity assessed prior to the first dose of the study treatment or sham. The first rule is to search for the most recent duplicate (i.e., 2 tests on 1 day) prior to dosing. The second rule is that, if there are no such duplicates (i.e., 2 tests on 1 day), the most recent 2 results will be used for baseline evaluation. After determining the most recent 2 results, the largest (best) BCVA ETDRS letter score prior to the administration of study treatment is selected as baseline. If only one assessment is available prior to the first administration of study treatment, that assessment will be used as the baseline value.

- 4.3. Data Handling
- 4.3.1. General

PQ-421a-004 Abbreviated SAP Version: 1.0, Date: 09-Sep-2022

Unless otherwise noted, the data reported in the listings will be as reported on the electronic case report form.

4.4. General Statistical Methods

All output will be incorporated into Rich Text Format (RTF) files and bookmarked PDFs, sorted and labeled according to the International Conference on Harmonisation (ICH) recommendations, and formatted to the appropriate page size(s).

Tabulations will be produced for appropriate disposition and demographic characteristics.

For measurements of continuous variables, summary statistics of absolute values will be reported and will include n, mean, standard deviation, median, and minimum and maximum values. The number of missing values will be displayed in parenthesis next to 'n'. Mean, standard deviation, median, will be presented with one more decimal place compared to the raw data, and minimum and maximum will be presented with the same number of decimal places as the raw data.

For categorical variables, summary tabulations of the number and percentage within each category of the parameter will be presented (as well as the number for missing data). Denominator for percentages is column N. Percentages will be rounded to one decimal place. Therefore, there may be cases where for instance the total of the percentages does not exactly equal 100%.

Where appropriate, data will be listed by eye (i.e., TE, CE).

In summary tables the study treatments will be presented in the following order: 'Shamprocedure', Ultevursen 60/60 μ g', 'Ultevursen 180/60 μ g', and if appropriate, 'All Subjects'.

4.5. Study Population

4.5.1. Subject Disposition

Subject disposition, including the number of screened subjects, the number of subjects failed screening, the number of randomized subjects, the number of subjects who received study treatment in the TE, the number of subjects who received study treatment in the CE, who completed the study and the number of subjects who discontinued from the study, along with the reasons will be summarized by treatment group.

PQ-421a-004 Abbreviated SAP Version: 1.0, Date: 09-Sep-2022

A listing of subject disposition will be generated, including the reason for premature study or treatment discontinuation, if applicable.

A listing of screen failure data will also be provided.

4.5.2. Demographic and Baseline Characteristics

Demographic and baseline characteristics, including age as collected, age category (Adult >=18 years, Children <18 years), gender, race, ethnicity, body weight (kg), height (cm), genotype (homozygous, heterozygous), randomization factor (syndromic, non-syndromic) and baseline BCVA (ETDRS letter score for both TE and CE), will be summarized for the Safety Population by treatment group using descriptive statistics.

4.6. Safety – Adverse events

A treatment-emergent AE (TEAE) is defined as an event that was not present prior to administration of the dose of study drug (ultevursen or sham-procedure) and present after the dose or if it represents the exacerbation of an event that was present prior to the dose.

Adverse events will be summarized by treatment group separately as follows:

- For non-ocular AE:
 - by subject, therefore, in any tabulation, a subject contributes only once to the count for a given adverse event (System Organ Class [SOC] or Preferred Term [PT])
 - o and during the overall study period (i.e., up to the last visit for the last subject).
 - Time to onset will be calculated in hours, relative to the last dose received, irrespective of which eye received the last dose (i.e., TE or CE).
- For ocular AE:
 - by eye frequencies, separately for the TE and the CE, therefore, in any tabulation, an eye contributes only once to the count for a given AE (by SOC or PT). AEs that are reported in both eyes (i.e., OU) will be reported individual by eye in the tabular summaries.
 - o and during the overall study period (i.e., up to the last visit for the last subject).
 - Time to onset will be calculated in hours, relative to the last dose received in the eye experiencing the ocular AE.

Unless otherwise stated, any summary of any type of TEAEs which includes the SOC and PT of the events will order the SOC and the PTs within the SOC by descending incidence of PT.

The following summary tables will be produced separately according to the type of AEs (ocular/non-ocular where applicable) as defined above:

- Overview of Ocular Adverse Events for Treatment Eye during the overall study period (Safety Population)
- Overview of Ocular Adverse Events for Contralateral Eye during the overall study period (Safety Population)
- Overview of Non-Ocular Adverse Events during the overall study period (Safety Population)
- Summary of Ocular Treatment-Emergent Adverse Events for Treatment Eye during the overall study period by MedDRA System Organ Class and Preferred Term (Safety Population)
- Summary of Ocular Treatment-Emergent Adverse Events for Contralateral Eye during the overall study period by MedDRA System Organ Class and Preferred Term (Safety Population).
- SAEs
- AESIs

4.6.1. Partial and Missing Date/Time for Adverse Events

Imputation of missing/partial AE date/time will be done only to identify TEAEs.

AE onset dates

- Partially missing onset date/time will be imputed as follows:
 - When only Day is missing:
 - If Month & Year of the onset date are the same as Month & Year of the first administration date, the imputed onset date will be imputed as the minimum of the first administration date/time and the AE resolution date (imputed if needed).
 - Otherwise, the missing day will be replaced by "1."

• When Day & Month are missing:

• If Year of the onset date is the same as Year of the first administration date, the imputed onset date will be imputed as the minimum of the first administration date/time and the AE end date (imputed if needed).

• Otherwise, the missing Day & Month will be replaced by "01 JAN."

• If a partial AE start date is consistent with the actual start date being on Day 1, and either the AE end date information is completely missing, or the complete or imputed AE end date/time information indicates that the AE did not end before Day 1, the imputed AE start date will be Day 1 in the following scenarios:

• The AE start time is missing (the AE will be flagged as treatment-emergent following the first dose of study treatment)

• The AE start time is after the date/time of first dosing of study treatment on Day 1 (the AE will be flagged as treatment-emergent following the first dose of study treatment)

• The AE start time is before the time of first dosing of study treatment on Day 1, and imputing the AE start date as Day 2 instead of Day 1 would be inconsistent with the partially recorded AE start date (e.g., the calendar month for Day 2 is not the same as for Day 1), or with the complete or imputed AE end date/time (in this case, the AE will not be flagged as treatment-emergent following the first dose of study treatment).

• Missing start time will be imputed with the time of administration if the day of AE start date and administration are identical, or with 00:00 otherwise.

Completely missing onset dates for AEs will be imputed by the first administration date and the AE will be considered as treatment-emergent, unless the end date/time of the AE (imputed if needed) or the end year of the AE (if day and month are missing) is entered and is before the first administration date. If the end date/time is before the first administration date, the AE will not be considered as treatment-emergent

AE end dates

• If Day only is missing, incomplete end dates will be replaced by the last day of the month if it is not resulting in a date later than the date of the subject's last visit. In the latter case, the date of the subject's last visit will be used to impute the incomplete end date.

• If Day & Month are missing, Day & Month will be replaced by 31DEC if it is not resulting in a date later than the date of the subject's last visit. In the latter case, the date of the subject's last visit will be used to impute the incomplete end date.

• If the AE end date is completely missing, the AE will be assumed to be ongoing on the date of the subject's last visit and the incomplete end date will not be imputed.

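### SAP 4.6.1 tests whether an AE ended before Day 1, not before the first dose, so some events that were over before dosing are flagged treatment-emergent

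*SAP*

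**What the plan says.** SAP 4.6 defines a TEAE as "an event that was not present prior to administration of the dose of study drug (ultevursen or sham-procedure) and present after the dose", or as the worsening of something already there before the dose. SAP 4.6.1 states a single purpose for its rules: "Imputation of missing/partial AE date/time will be done only to identify TEAEs".

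Four of those rules can touch an AE that ended on the dosing day:

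- **Minimum rule.** If the day is missing and month and year match the first administration, "the imputed onset date will be imputed as the minimum of the first administration date/time and the AE resolution date (imputed if needed". A parallel rule covers a missing day and month.
- **Day 1 rule.** It applies if the partial start could be Day 1 and the end is either wholly missing or "the complete or imputed AE end date/time information indicates that the AE did not end before Day 1". Its first scenario is "The AE start time is missing (the AE will be flagged as treatment-emergent following the first dose of study treatment"). Its second gives the same flag when the start time is later than dosing. Its third gives no flag when the start time is before dosing and a Day 2 start is impossible.
- **Missing-start-time rule.** "Missing start time will be imputed with the time of administration if the day of AE start date and administration are identical".
- **Completely missing onset.** The AE counts as treatment-emergent unless its end falls before the first administration date.

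**The concern.** The definition asks whether the event was absent before the dose and present after it. The Day 1 rule and the completely-missing-onset rule ask only whether the event ended before the calendar day of the dose, and the missing-start-time rule does not look at the end at all. An event that ended on the morning of Day 1, before the injection or sham, passes all three, although its recorded end time shows that it cannot be treatment-emergent. It cannot qualify as an exacerbation either, because it was over.

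Such events can exist. Protocol 9.2.1 makes events before treatment reportable when a protocol procedure caused them, and its examples are blood draws and sedation before the injection. Protocol 9.4.1 intends events before first dose to be captured as non-treatment-emergent.

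At stake is the correctness of the TEAE flag, which is the only product of SAP 4.6.1, and whether two programmers following the text would set it alike.

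**Working it through.** The plan gives no figure to reproduce. The check applies each rule literally to test records.

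**Inputs.** The rules and definition are those of SAP 4.6 and 4.6.1. First dose is on Day 1 (SAP 2.1). The clock times are illustrative assumptions: dose on 15 March at 10:00, and ends of 14 March 20:00, 15 March 08:00 or 15 March 20:00. For partial starts the day in March is unknown and the start time is missing, 07:00 or 15:00.

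**Case (a): partial start date.** The minimum rule is run in two ways. The date/time reading takes the earlier of the dose date/time and the recorded end date/time. The date-only reading takes the earlier date, then uses the recorded start time or, if there is none, the missing-start-time rule. TE means treatment-emergent.

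| End | Start time | Day 1 rule | Minimum rule, date/time | Minimum rule, date only | Definition |
|---|---|---|---|---|---|
| 15 Mar 08:00 | missing | TE | not TE | TE | not TE |
| 15 Mar 08:00 | 15:00 | TE | not TE | TE | not TE |
| 15 Mar 08:00 | 07:00 | not TE | not TE | not TE | not TE |
| 14 Mar 20:00 | any of the three | not triggered | not TE | not TE | not TE |
| 15 Mar 20:00 | missing or 15:00 | TE | TE | TE | can be TE |
| 15 Mar 20:00 | 07:00 | not TE | TE | not TE | began before dose |

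Row 1: the event ended 10:00 − 08:00 = 2 hours before the dose. The end is not before Day 1 and the start time is missing, so the Day 1 rule flags it. On the date/time reading the minimum rule gives min(10:00, 08:00) = 08:00, which is before the dose, so no flag. On the date-only reading the minimum is 15 March, the start time is filled with 10:00, and the event is flagged.

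Row 2: the Day 1 rule puts onset at 15:00 on Day 1, which is 15:00 − 08:00 = 7 hours after the recorded end. The rule checks only that the partial start date could be Day 1. It does not check that a Day 1 start at that time would precede the end.

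Row 3: with a recorded pre-dose start time, the third scenario gives the right answer.

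Row 6: the latest possible start is 15 March 07:00, so the event began before the dose. The third scenario is right here, and the minimum rule read as date/time is not. This is why precedence needs stating.

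**Case (b): start 15 March, no start time, end 15 March 08:00.** The missing-start-time rule sets onset to 10:00, which is 2 hours after the recorded end, and the event is flagged. No partial date is needed.

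**Case (c): onset completely missing, end 15 March 08:00.** The end is not before the administration date of 15 March, so the event is flagged.

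**After the change of cut-off.** With the date/time of first dosing as the test, the Day 1 rule is no longer triggered by an end of 15 March 08:00, and case (c) gives not TE. Rows 1 and 2 then fall back to the minimum rule, which gives not TE only if it is a date/time comparison. Under the Day 1 and completely-missing-onset rules, the flags for ends of 14 March 20:00 and 15 March 20:00 do not change.

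**The case against.** Several objections have weight.

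- **The opposite flags depend on a reading.** A reader might infer that the minimum rule and the Day 1 rule always contradict each other for row 1. The minimum rule imputes an onset date and compares with a resolution date, so a date-only reading is possible, and then both rules flag the event. This stands: the conflict is conditional. The rule's own reference to a date/time for first administration favours the date/time reading, and the shared flag on the other reading is still wrong.
- **A Day 1 end with no time.** A reader might infer a second conflict by treating the bare end date as midnight. The documents do not support that. SAP 4.6.1 uses 00:00 only for missing start times on non-dosing days and gives no end-time imputation.
- **Order of coding.** The Day 1 rule is more specific, comes later and states the flag outright, so reading it as a refinement is natural. The lack of a precedence sentence is a gap, but it does not make the result arbitrary.
- **Defaulting to treatment-emergent is cautious.** That is sound when timing is unknown. Here the recorded end time settles the matter, and the Day 1 rule already compares clock times for the start.
- **The records are unusual.** An end known to the hour with an unknown start day will be uncommon. Procedure events seen by staff would mostly have a complete start date, which leaves case (b). The protocol's examples would also be mostly non-ocular, and SAP 4.6 lists no non-ocular TEAE table by SOC and PT.
- **Little depends on it.** SAP 5 drops formal analysis, the rules apply alike in every arm, and SAP 4.7 lists all AEs. This limits the importance, but the wording is still wrong.

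**Conclusion.** The defect is real and narrow. For an AE recorded as ending on Day 1 before the dose, SAP 4.6.1 sets a flag that contradicts SAP 4.6 in cases (a), (b) and (c). In case (a) the start time must be missing or later than the dose time. Whether the minimum rule then disagrees with the Day 1 rule turns on reading it as a date/time comparison.

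The error over-counts TEAEs and hides none. It can reach the AE overview tables and the ocular TEAE tables listed in SAP 4.6. A reader might want to turn it into a shift in TEAE percentages using 40 per arm. The documents do not support that: 40 is the planned arm size in a trial that was stopped early, and nothing indicates how many records have this pattern. The conclusion rests on a literal reading of the rules and on end times being recorded for at least some Day 1 events. It is a minor correction.

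**What to change.** In SAP 4.6.1:

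1. In the Day 1 rule, replace the Day 1 cut-off in the end test with the date/time of first dosing. Use the same cut-off for completely missing onset.
2. Word both minimum rules as date/time comparisons. Otherwise a record that fails the new end test can still be flagged through them.
3. In the missing-start-time rule, impute the dose time only if the recorded end is not before it. If it is, impute the recorded end time and set the flag to not treatment-emergent.
4. State that an AE ending on Day 1 with no end time is treated as ending after dosing.
5. State that the Day 1 rule takes precedence over the minimum rule when both apply.

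The cost is a wording change and one condition in the TEAE flag program. No new data are needed.

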4.7. Other Data Listings to be Generated

The following by-subject data listings for the Safety Population will be provided:

- Subject Disposition
- Screen Failures (All Screened Subjects)
- Demographic and Baseline Characteristics (Safety Population)
- Non-Ocular Medical History (Safety Population)
- Ocular Medical History (Safety Population)
- Study Drug Administration of the TE (Safety Population)
- Study Drug Administration of the CE (Safety Population)
- BCVA Based on ETDRS (Safety Population)
- Low Luminance Visual Acuity (LLVA) (Safety Population)
- Full-field Stimulus Testing (FST) (Safety Population)
- Spectral Domain Optical Coherence Tomography (SD-OCT) (Safety Population)
- Static perimetry (Safety population)
- Patient Global Impressions of Severity (PGI-S) and Patient Global Impressions of Change (PGI-C) (Safety Population)
- Michigan Retinal Disease Questionnaire (Safety Population)
- Ophthalmic exam (Safety Population)
- Non-Ocular Adverse Events (Safety Population)
- Ocular Adverse Events (Safety Population)
- Prior and/or Concomitant Medications (Safety Population)

• Laboratory results: Hematology, Coagulation, Chemistry and Urinalysis (Safety Population)

5. CHANGES TO PLANNED ANALYSES

As the study is prematurely stopped by Sponsor's decision, no formal statistical analysis will be produced. Only disposition, demographic and baseline characteristics, and overview of AEs will be summarized in tables. By-subjects data listings will be produced based on raw data.

6. **REFERENCES**

1. International Council on Harmonization, Statistical Principles for Clinical Trials (ICH E9)

7. APPENDICES

The shells of planned outputs are provided in a separate document (PQ-421a-004_List of Planned Outputs_V1.0).
